#### 5.1.4 Subgroup Analysis

The following subgroup variables are included in the subgroup analysis:

- Sex
- Age
  - o ≤50 vs. >50 Years
  - o <75 vs. >75 Years
- Site of anastomosis (Recorded on the Procedure Overview eCRF page: "Which Artery/Vein was Used to Create the endoAVF"):
  - O Ulnar / Radial / Other
- Location of arterial procedure access (Recorded on the Procedure Overview eCRF page: "Which Artery was Used to Gain Access"):
  - o Brachial / Ulnar / Radial / Other
  - o Wrist Artery Access (Ulnar & Radial) / Non-Wrist Artery Access (Brachial)
- Second Stage Procedures identified at Index Procedure (Recorded on the Procedure Overview eCRF page: "Is a Second Stage Procedure Planned?")

## 5.2 Secondary Endpoints

#### **5.2.1** Safety

The proportion of participants with freedom from CEC adjudicated device-related or procedure-related SAEs will also be assessed through 6-months (Day 180) and 24-months (Day 730) post creation, using the same definition as the primary safety endpoint. The proportion and the 95% CI will be provided using the Clopper-Pearson method. Additionally, for exploratory purposes, the endpoint will be assessed through 6-weeks, 3-months, 12 months, and 18 months post creation.

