4.2.1 Safety

• Device and Procedure Related SAEs

The proportion of participants with freedom from CEC adjudicated device-related or procedure-related SAEs (refer to Section 8 for definitions). This endpoint will be assessed through 6- and 24-months post creation.

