4.4 Applicable Endpoint Definitions

Access Abandonment (permanent abandonment) is defined as the point at which the access can no longer be used for one or two needle prescribed HD as it may be unable to provide adequate flows and / or is deemed unsafe for the participant, and the associated problem cannot be corrected by any further intervention, including medical, surgical, or endovascular interventions or rest.^{8,19} Participants with an abandoned index AVF will continue with follow-up through 24-months and data will be collected on safety and interventions.

A HD AV access is not considered abandoned:

- If the participant discontinues use of the AV access due to kidney transplant, initiation of PD, or participant preference.
- During the maturation period or while waiting for a second stage procedure unless the principal investigator (PI) determines the participant requires and they then receive an alternative HD vascular access.

- During planned interventions, including transposition.
- If all reasonable efforts have not been attempted (and documented) to improve the condition of the access for it to be used.

A discontinuation of use of the clinical investigation AVF for any reason that does not meet this definition of access abandonment will be considered a temporary interruption.

Access Circuit Censoring Events include participant transfer to PD, kidney transplantation or the event of a participants premature discontinuation in the investigation due to withdrawn consent, withdrawal by PI, Lost to Follow-Up (LTF), or participant death (refer to Section 6.5 for definitions).

Adjunctive Procedure(s): Procedure(s) completed during the index procedure (prior to leaving the procedure room) as part of Standard-of-Care (SOC) procedures. These may include procedures to facilitate maturation and / or cannulation of the AVF, procedures to maintain use of the AVF, procedures to ensure HD continuity, as well as procedures to address AFs.

Second Stage Procedure(s): Facilitation Interventions (as defined below) intended to support the cannulation of arterialized vein segments that are determined to be needed a priori to or at the time of the index procedure (i.e. pre-planned facilitation interventions intended to support cannulation). Second stage procedures will not count against the intervention or patency endpoints and will require completion of the Second Stage Procedures eCRF.

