6.2.1 Clinical Investigation Treatment

After the PI, or authorized designee(s), has determined that the participant is eligible for participation based on the criteria listed in Section 5.1, has completed all of the required baseline procedures, the participant may be treated using the WavelinQTM EndoAVF System. It is recommended that eligibility for all participants (including DUS and determination of any central venous lesions) be verified at the time of the index procedure prior to the point of treatment with the WavelinQTM EndoAVF System if anatomical eligibility verification was originally completed prior to the index procedure.

Examinations, evaluations, procedural preparation, angiography, treatment, and hospital / facility discharge procedures will be conducted per the investigational site's SOC.

The treatment using the WavelinQTM EndoAVF System, will be per the investigational site's SOC and must adhere to the device IFU. Operators of the WavelinQTM EndoAVF System must complete BD-Sponsored device training and must be approved by the Sponsor as an operator in writing before conducting a clinical investigation index procedure on enrolled participants (refer also to Section 12.2). For detailed information on device use and procedural medication recommendations, reference the IFU.

NOTE: If the participant has more than one brachial vein, embolization of one of the brachial veins is recommended to divert flow to the superficial veins to facilitate maturation of the endoAVF.

NOTE: Angiographic images collected during the index procedure including documentation of the final result must be submitted to the Sponsor. Refer to the investigational site's regulatory binder for guidelines on the collection of all DUS and angiographic images captured during the index procedure and details on submission of these images to the Sponsor / Core Lab.

A *treated participant* in this clinical investigation is defined as a participant that has met all eligibility criteria (as listed in Section 5.1), into whom the WavelinQTM EndoAVF system was introduced, and in whom procedure success was achieved (as defined in Section 4.3). Treated participants will continue clinical investigation participation through the clinical investigation's 24-month follow-up period.

Participants into whom the WavelinQTM EndoAVF System was introduced but procedure success was not achieved will be followed through the 30-day follow-up to assess for any safety events and interventions.

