7.3 Sample Size Considerations

The sample size for the study of one-hundred and fifty (150) treated participants was established to assure adequate power for the primary safety and effectiveness endpoints as

well as to result in a sufficient sample size (when accounting for attrition) for assessment of the secondary and exploratory endpoints, specifically for those that only apply to subsets of the overall population (i.e. the incident population and wrist arterial procedure access population).

- 1) *Primary Safety Endpoint* The proportion of participants with freedom from device-or procedure-related SAEs through 30 days (ITT Population).
 - Assumptions:
 - The freedom from device- or procedure-related SAE rate for AVFs created using the WavelinQTM EndoAVF System is estimated at 92.6% through 30 days based on pre-market data;
 - The PG is set at 82.6% using a 10% non-inferiority margin;
 - The rate of attrition through 30 days is assumed to be 10%; and
 - o The Type 1 error is 0.05 (two-sided).
 - Sample Size:
 - A sample size of 150 treated participants [135 evaluable] will give over 92.5% power with a two-sided type I error of 0.05 as calculated using PASS 2019 (One Proportion Exact Test).
- 2) Primary Effectiveness Endpoint Interventions Post Creation to Facilitate AVF Use and / or Maintain AVF Use (Facilitation and / or Maintenance Interventions) through the Timepoint of the 6-Month Follow-Up of the Last Active Treated Participant (AT Population)
 - Assumptions:
 - The number of interventions post creation to facilitate AVF use and / or maintain AVF use after AVF creation using the WavelinQTM EndoAVF System is estimated at 3.0 / PY, a conservative assumption based on pre-market data;
 - The PG is set at 5 / PY to align with the targets and recommendations of the 2019 update of the KDOQI Clinical Practice Guideline for Vascular Access of < 2 interventions to facilitate and < 3 interventions to maintain AVF use;
 - The rate of attrition through 6-, 12-, and 24-months, including lost to followup, death, and other clinical investigation premature withdrawals is assumed to be 20%, 40%, and 60%, respectively; and
 - o The Type 1 error is 0.05 (two-sided).
 - Sample Size:
 - O A sample size of 150 treated participants, yielding more than 100 PY by the time the last active treated participant completes their 6-month follow-up, will give over 99% power with a two-sided type I error of 0.05 as calculated using PASS 2019 (One-Sample Poisson Rate Test).

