7.7.3 Handling of Missing Data

Investigation endpoints may have missing data due to a participant's withdrawal of consent, the withdrawal of a participant by the PI, a participant loss to follow-up and the death of a participant. Data may also be missing from investigation endpoints due to deviations and / or missing data collection. It is important to minimize missing data by all means and to always record the reason for omission.

For the primary safety endpoint, a conservative approach will be used for the handling of missing data: If a participant has a specified event (device-related or procedure-related SAE), the participant will be included irrespective of if the participant prematurely discontinues prior to the 30 day timepoint; if a participant prematurely discontinues before 30 days without the occurrence of a specified event, the participant will be considered not evaluable and will not be included in the primary safety endpoint analysis.

For the primary effectiveness endpoint, the Poisson regression model will be used to analyze the data. In the Poisson regression model, missing data handling is a standard part of the analysis: If a treated participant prematurely discontinues prior to the data cut, that participant's study duration will be considered as the period of time between the index procedure and their premature discontinuation, and the corresponding number of facilitation and/or maintenance interventions in that specific duration will be used for analysis.

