## 5 Statistical Analysis/Calculations

## 5.1 Primary Endpoints

## 5.1.1 Primary Safety Endpoint

The primary safety endpoint is the proportion of participants with freedom from CEC adjudicated device- or procedure-related SAEs through 30 days.

The primary safety endpoint will be evaluated against a PG of 82.6%, which was set with a 10% non-inferiority margin of the estimated 92.6% through 30 days derived from premarket data from the prior clinical investigations evaluating the WavelinQTM EndoAVF System.

The primary safety endpoint will be evaluated by the following hypothesis:

- H₀: The primary safety endpoint of proportion of AVF with freedom from SAE for the WavelinQTM EndoAVF System treated participants through 30 days (PWS) is less than or equal to that of the PG of 82.6%.
- H1: The primary safety endpoint of proportion of AVF with freedom from SAE for the WavelinQTM EndoAVF System treated participants through 30 days (PWS) is greater than that of the PG of 82.6%.

That is:

 $H_0$ :  $P_{WS} \le 82.6\%$  $H_1$ :  $P_{WS} > 82.6\%$ 

Rejection of the null hypothesis will signify that the 30-day safety of the WavelinQTM EndoAVF System is greater than the safety PG of 82.6%.

The device- or procedure-related SAE will be identified if:

On the Adverse Event Adjudication page, Serious (SAE) is checked as Yes, and Relationship to Study Device is or Relationship to Procedure is Possibly Related or Definitely Related.

The binary definition is shown as below:

- If the device or procedure-related SAE start date occurs before or on Day 30, the participant is considered as having an event.
- If the participant discontinued before the beginning of 30-day follow-up visit window (30-5 = Day 25) without having the device- or procedure-related SAE, the participant is considered not evaluable and will not be included in the analysis.
- Otherwise, if the participant is in the investigation without having the device-related SAE and has passed the 30-day follow-up visit by the cutoff date of database lock, the participant is considered as not having an event.

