The primary safety analysis will be conducted based on evaluable participants only in the ITT population. A two-sided p-value will be derived based on an exact binomial test comparing to the PG of 82.6% and the 95% two-sided confidence interval (CI) will be provided using the Clopper-Pearson method. The WavelinQTM EndoAVF System will be considered to have achieved the safety objective and will reject the null hypothesis if the two-sided p-value is less than 0.05, equivalently, the lower bound of the 95% CI is greater than 82.6%. The primary safety analysis will be repeated on the PP population.

Additionally, as a supportive analysis, Kaplan-Meier (KM) analysis will be used to analyze the primary safety endpoint.

- If the device or procedure-related SAE occurs before or on Day 30, the participant is considered as having the event at the corresponding start date.
- If the participant was transferred to PD, or had a kidney transplant, or had permanent abandonment, or had access discontinuation, or discontinued before Day 30 without having device or procedure-related SAE, the participant is considered as censored at the earliest date among these events (i.e., PD start date, kidney

transplant date, date of permanent abandonment, date of access discontinuation, last date of available study data including the unscheduled visit date).

• Otherwise, if the participant did not have a device or procedure-related SAE and has passed Day 30 by the cutoff date of database lock, the participant will be censored at Day 30 for this analysis.

The analysis will be evaluated on the ITT population. The number of participants with events, number of participants censored, time to event (days), and proportion of participants with events along with the 95% CI will be presented.

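### SAP 5.2.1 carries the 30-day evaluable-only rule to Day 730, inflating the 24-month related-SAE risk about 1.5- to 2-fold at the plan's own attrition; SAP 5.2.4 replaces a censored time with a binary proportion

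*SAP*

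**What the plan says.** **Safety.** Protocol 4.2.1 defines the secondary endpoint as "The proportion of participants with freedom from CEC adjudicated device-related or procedure-related SAEs", assessed through 6 and 24 months. SAP 5.2.1 assesses it at Day 180 and Day 730; its wording is "post creation, using the same definition as the primary safety endpoint. The proportion and the 95% CI will be provided using the Clopper-Pearson method". That borrowed definition is in SAP 5.1.1. An SAE on or before the horizon counts as an event. For someone who discontinues event-free before the visit window opens, "the participant is considered not evaluable and will not be included in the analysis". Protocol 7.7.3 states this exclusion for the primary safety endpoint alone: "if a participant prematurely discontinues before 30 days without the occurrence of a specified event, the participant will be considered not evaluable".

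Protocol 7.3 and SAP 2.4 assume 10% attrition through 30 days. For 6, 12 and 24 months, losses including death and "premature withdrawals is assumed to be 20%, 40%, and 60%, respectively". SAP 5.1.1 adds a supportive Kaplan-Meier (KM) analysis, but it covers only the 30-day endpoint.

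The safety population is ITT. It includes about 10 failed creations (protocol section 3), and participants in whom "procedure success was not achieved will be followed through the 30-day follow-up" have no later visits.

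**Functional patency.** Protocol 4.2.2 defines cumulative functional patency as the time from first successful 2-needle use to abandonment, with censoring events fixed in advance, assessed through 12 months after creation. Protocol 7.5 prescribes KM for time-to-event secondary endpoints. SAP 5.2.4 uses a binary outcome and a Clopper-Pearson interval. It removes participants with PD transfer, transplant, access discontinuation or early exit before the window opens without abandonment.

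**The concern.** An evaluable-only proportion treats the two outcomes differently. An event observed at any time stays in both numerator and denominator. An event-free participant stays only if followed to the window. As losses accumulate, the denominator shrinks around a fixed set of events and the reported risk rises. With 10% lost by Day 30 this matters little. With 60% lost by 24 months, more than half the participants disappear, none of them with an observed event.

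The 24-month figure is the plan's long-term safety result. SAP 5.2.1 also reports 6 weeks and 3, 12 and 18 months, so the tables could show related-SAE risk climbing through follow-up when only the denominator had changed.

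For patency, the SAP departs from the method the protocol prescribes and turns the protocol's censoring events (PD transfer, transplant, premature discontinuation) into exclusions. The clock starts at first use but the horizon is counted from creation, so a late starter contributes less time to the 12-month figure than an early one. The KM analysis of abandonment in SAP 5.3.8 starts at creation and does not replace this endpoint.

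**Working it through.** **Plan's own figure.** The documents give no 24-month projection. The 30-day power does reproduce: with 135 evaluable, the exact test rejects at 121 or more event-free, attained one-sided alpha is 0.0162, and power at 92.6% is 0.925.

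**Inputs from the plan.** Attrition is 20/40/60% at 6/12/24 months, with and without 10% by Day 30; N = 150; the 30-day event risk is 100 − 92.6 = 7.4%. The 24-month window is ±30 days, so by analogy with the Day 25 cut in SAP 5.1.1 it opens at Day 700.

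**Assumptions.** Dropout is independent of events and linear between the plan's points. Event timing is not given, so it is varied.

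**Formula.** Reported risk = observed events / (observed events + non-events retained to Day 700).

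**Retention at Day 700.** 0.60 − 0.20 × (700 − 365)/365 = 41.6%.

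**Hand check, 7.4% all in month 1.**
- True events: 150 × 0.074 = 11.1. Dropout by Day 30 is 20% × 30/180 = 3.3%, averaging about 1.7% over the month, so about 10.9 are observed.
- Non-events retained: 138.9 × 0.416 = 57.8.
- Reported risk: 10.9/(10.9 + 57.8) = 15.9%. With 10% lost by Day 30 it is 15.4%.

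| True 24-month risk | Event timing | Reported risk | Ratio |
|---|---|---|---|
| 7.4% | all by Day 30 | 15.4–15.9% | about 2.1 |
| 7.4% | constant hazard | about 11% | about 1.5 |
| 10% | 7.4% by Day 30, rest later | 18.8–19.2% | about 1.9 |
| 10% | constant hazard to all in month 1 | 14.7–20.8% | 1.5–2.1 |
| 15% | 7.4% by Day 30, rest later | 25.0–25.5% | about 1.7 |
| 20% | 7.4% by Day 30, rest later | 31.0–31.4% | about 1.6 |

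Between 53% and 57% of participants are excluded for a true risk of 7.4%.

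**Interval coverage** (4,000 simulated trials of 150, true risk 7.4%). The Clopper-Pearson 95% interval covers the truth in 42–46% of trials with month-1 events and 84–85% at constant hazard. KM covers it in 95–96%.

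**Six months.** Retention at Day 150 is 82–83%. A true 10% is reported as 10.5–11.6%.

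**Spurious trend.** With 7.4% by Day 30 and no related SAE afterwards, the plan would report about 8.5–8.6% at 6 months and 15.4–15.9% at 24 months.

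**Failed creations.** If the 10 count only when they have an event by Day 30 (10 × 0.074 = 0.74), the early-event figures become (10.9 + 0.74)/(10.9 + 0.74 + 57.8), about 16.7–16.8%, and in the other variant 16.3%. At constant hazard the change is about 0.1 point.

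**Functional patency.** No 12-month rate is given, so rates and start dates are assumed: exponential loss; first use at Day 0, Day 30–180 or Day 60–330; SAP windows Day 335 and Day 395. Against the post-creation horizon the error is zero at 100% patency, 1–3 points too low at 90%, and 3–7 too low at 70%. Against 12 months from first use, late starts can reverse the sign (−3 to +4 points at 90%).

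**The case against.** - **No protocol breach on safety.** Protocol 4.2.1 calls the endpoint a proportion, and protocol 7.5 prescribes counts and percentages for categorical variables. This stands: the safety point rests on bias. A KM estimate still reports a proportion free of events.
- **Descriptive and conservative.** No test, performance goal or sample size depends on Day 730, and the error runs against the device. This limits the priority. It does not make a rate near twice the truth, with an interval that can miss it more often than not, a sound description.
- **The size is conditional.** The 60% is a planning assumption listed under the effectiveness endpoint. With an assumed 10/20/30% attrition the same formula gives 1.13–1.36-fold, and with 5/10/20% it gives 1.09–1.21-fold. Constant hazard at 7.4% over 24 months sits badly with 7.4% already by Day 30; on the plan's own 30-day figure the upper part of the range is more likely. KM's good coverage follows from simulating independent dropout.
- **Failed creations may be settled elsewhere.** The derived-data specification (SAP Appendix 2) is listed by title only and may classify them. This is fair, and the effect is at most about 1 point.
- **Patency may hardly move.** The earlier studies reported 100% functional patency through 6 months (protocol 2.1.2), where the error is zero. The horizon counted from creation is also the protocol's own wording. Both stand, but the conflict of method remains.

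**Conclusion.** Both parts hold.

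For safety, the rule is tolerable at 30 days, has a small effect at 6 months, and is wrong as the main estimate at 24 months. At the plan's own attrition the reported risk is about 1.5 times the truth if events are evenly spread and about 2 times if most fall in month 1. This assumes dropout unrelated to events, and it shrinks if attrition is lower.

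Death does not rescue the rule. If 25% or 50% of attrition were deaths (assumed), a net constant-hazard risk of 10% would correspond to a cumulative incidence of 8.9% or 8.0%, further still from the 14.7–15% reported.

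For functional patency, the SAP conflicts with protocol 4.2.2 and 7.5. The likely effect is a few points or less, on assumed inputs.

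The change should be made, but the primary analyses do not depend on it.

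**What to change.** **SAP 5.2.1.** Make KM in the ITT population the main estimate at Day 180 and Day 730, and name the confidence-interval method. Censor at last contact, which is the 30-day follow-up for failed creations. Do not reuse the supportive rule in SAP 5.1.1, which censors those who "had permanent abandonment, or had access discontinuation, or discontinued before Day 30": protocol 4.4 says "Participants with an abandoned index AVF will continue with follow-up through 24-months and data will be collected on safety and interventions", so later related SAEs would be discarded. State that unrelated death is censored, or add a cumulative-incidence sensitivity analysis with death as a competing event.

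**SAP 5.2.4.** Use KM from first successful 2-needle use with the censoring events of protocol 4.4. Reconcile the time origin with the 12-months-after-creation horizon, in the protocol as well as the SAP.

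Keep both binary tables as supportive, with the number excluded shown.

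**Cost.** SAP wording, the derived-data specification and table shells. The dates needed are already collected.
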